- Diet exclusions: Food allergies, special dietary restrictions, routine consumption of less than 3 meals/day or dietary habits that may undermine compliance to dietary protocol, routine ingestion of more than 2 sugar-sweetened beverages or 1 alcoholic beverage/day, unwillingness to consume any food on study menu
- Veins that are assessed by the R.N.s as being unsuitable for long-term infusions and multiple blood draws from a catheter.
- Pre-existing claustrophobia or metal implants that preclude MRI
- Any other condition that, in the opinion of the investigators, would put the subject at risk
- A recent positive COVID-19 test

We will exclude individuals from each of the following special populations:

- Adults unable to consent
- Individuals who are not yet adults (infants, children, teenagers < 18 years)
- Pregnant women
- Prisoners

We will also exclude non-English speakers because study procedures can only be implemented with proficiency in English. At the current time we do not have staff that are proficient in any other language than English and we do not have the funds to hire extra staff with bi-lingual

The effects of orange juice compared with sugar-sweetened beverage on risk factors and metabolic processes associated with the development of cardiovascular disease and type 2 diabetes

skills. This is also true for the staff at Touro University, where the 12-hour blood collection procedures are conducted.

Effective and clear communication between the study staff and between the subjects is essential in order to properly implement the experimental and dietary protocols required for this study. Before confirming their willingness to participate in this study, the subjects must have a clear understanding of what is required of them in terms of time commitment, diet commitment, and also an understanding of procedures that they will undergo. For example, it is very important that potential subjects clearly understand that we need to know if they have metal implants in their bodies because certain metal implants can cause great harm to them during magnetic resonance imaging. Potential subjects need to clearly understand that this study requires many blood samples and realize that if the insertions required for needle-stick collections or catheters makes them nervous or unhappy, this study is not for them.

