Anyone coming onto campus (students, employees or visitors) is required to follow the university COVID-19 safety guidelines that are posted on the campus website: https://campusready.ucdavis.edu/, which may include filling out the UC Davis Daily Symptom Survey during each visit and completing COVID-19 testing. Additionally, participants will be required to wear a mask during all study interactions, have their temperature monitored and maintain a 6-foot distance when possible (e.g., except Registered Nurses performing blood draws). For transport by study staff in UCD vehicles to study procedure sites, participants will be provided and required to wear a KN95 or N95 mask, face shield and to sit 6 feet away from the driver and any other passenger.

General study design: The study is designed as a parallel, 6-week study with a 2-week baseline period during which all subjects consume the provided low-sugar baseline diet and a 4-week intervention period during which the experimental beverages are consumed along with a low-sugar diet.

Baseline (Week 1-2): All subjects will consume a provided, standardized, low sugar, energy-balanced diet for approximately 9-13 days. All experimental procedures are conducted. **Intervention (Week 3-6):** Subjects will be stratified by gender and normal weight/overweight status and randomized to one of the two groups listed below:

- **1.** Sugar-sweetened beverages (SSB): 25% of estimated Ereq/day as sucrose in water (11% weight/w/w), flavored with unsweetened Kool-Aid and divided into 3 servings/day.
- **2. Orange Juice (OJ)**: 25% of estimated Ereq/day as the carbohydrate in OJ divided into 3 servings/day.

Subjects will consume three provided beverages/day along with provided, standardized, energy-balanced meals and snacks for approximately 28-33 days. All experimental procedures are repeated.

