Beverage and meal pick-up/return: At appointments scheduled at their convenience, subjects will report to Ragle HNRC two times/week to pick up a 3- or 4-day supply of meals/snacks/beverages, and to return uneaten food and packaging. If Ragle HNRC is unavailable due to facility safety restrictions or schedules conflicts, the foyer at the entrance to Ragle HNRC will be used. Temperature will be measured using a contactless thermometer. Subject will be given a urine collection cup and and asked to provide a urine sample using the restroom in the foyer area. All exchanges of meal & beverage carrying cases and urine cup & urine sample will be conducted with both subject and study staff member wearing masks, face shields and maintaining a 6-foot distance at all time. Thus there will be a designated cart or area in the foyer upon which all carrying bag/supplies/samples will be set for dispensation or for turnin. The cart or area will also have a supply of sterile wipes and disposable gloves so all items can

The effects of orange juice compared with sugar-sweetened beverage on risk factors and metabolic processes associated with the development of cardiovascular disease and type 2 diabetes

be decontaminated prior to being picked up. Subjects who fail to pick up a new supply of meals/beverages (or make arrangements for it to be delivered to their homes) in time to allow for uninterrupted consumption as required by the protocol, will be dismissed from the study for non-compliance. Subject will need to fill out study diet report forms, physical activity questionnaires and food surveys. These forms will be made available to complete electronically and are used to assess diet palatability and quantity, activity level changes and to describe diet deviations. These reports will be reviewed by the Study Coordinator and communication through text, email or Zoom call will be used to discuss issues or request clarifications.

Compliance monitoring: The sweetened beverages will contain a biomarker (riboflavin). The biomarker will be assayed in urine collected 2 times/week during meal pick-up appointments. The subjects will be informed that they are being monitored for compliance, but not provided specifics as to the method. We have successfully used this method of enhancing compliance in three previous studies^{7, 14, 15}.

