To identify subjects who consume or consumed non-study foods that contained HFCS or cane sugar or consume alcoholic beverages during the study period, we will measure biomarkers for added sugar and alcohol intake. We will measure the delta ¹³C value of blood drops collected at baseline and at the end of 4 weeks of intervention. The Delta ¹³C content in the blood drop will be measured at the UCD Stable Isotope Facility. Delta ¹³C is a novel validated biomarker of added sugar intake because most plants have a low natural abundance of delta ¹³C, while that of corn and sugar cane is conspicuously higher ^{110, 111}. The foods with the highest amounts of delta ¹³C are pure corn products, and beverages, hard candies and desserts sweetened with HFCS or cane sugar. Sugar from sugar beets has a low natural abundance of delta ¹³C, therefore beet sugar will be used to sweeten the sucrose-sweetened beverages provided as part of the intervention. Delta ¹³C in blood is an indicator of added HFCS and sugar cane sucrose consumption over the prior 2 weeks ³. Because all the meals and snacks provided during the 6-week study have a very low HFCS and sugar cane content, and all subjects are consuming the same foods, all compliant subjects will exhibit low and comparable levels of blood delta ¹³C at both the end of the 2nd week and 6th week of study. Data from subjects with delta ¹³C blood values that are more than 2 standard deviations above the mean for all subjects will not be included in the statistical analyses.

To identify subjects who routinely consume alcohol we will assay urinary ethyl glucuronide (immunoassay, Thermo Scientific, Fremont, CA) in the urine samples collected at each meal pick-up visit. Detection of ethyl glucuronide in urine indicates recent alcohol consumption ¹¹² and is considered to be a specific, highly sensitive, and reliable marker of recent alcohol intake within the previous 5 days ⁴. Urinary ethyl glucuronide concentrations above the 500 ng/ml will be considered positive for alcohol intake. Urine will be monitored for alcohol intake upon collection, and subjects with positive values will be considered for dismissal. The subjects will be informed that they are being monitored for compliance to the requirement that they not consume non-study food, but will not be provided specifics as to the method.

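### The baseline delta-13C sample looks back about 1-5 days further than the stated study diet, so the automatic 2-SD exclusion can remove a compliant subject for sugar that was allowed before the study

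*Combined protocol and SAP*

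**What the plan says.** All references are to the combined protocol and SAP.

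- **Look-back of the sugar marker** (section 7, Compliance monitoring): delta-13C in blood "is an indicator of added HFCS and sugar cane sucrose consumption over the prior 2 weeks".
- **Sampling** (same section): "We will measure the delta ¹³C value of blood drops collected at baseline and at the end of 4 weeks of intervention".
- **Expectation** (same section): "all compliant subjects will exhibit low and comparable levels of blood delta ¹³C at both the end of the 2nd week and 6th week of" (weeks are counted from the start of the diet). Subjects whose value lies over 2 SD above the overall mean are left out of the statistical analyses. No sample is exempted, and the text does not say whether the mean and SD are taken per time point or pooled.
- **Length of the diets** (section 7, General study design): for baseline, "All subjects will consume a provided, standardized, low sugar, energy-balanced diet for approximately 9-13 days"; for the intervention, beverages with "standardized, energy-balanced meals and snacks for approximately 28-33 days".
- **Permitted habits before the study** (section 4, diet exclusions): a subject is excluded for "routine ingestion of more than 2 sugar-sweetened beverages or 1 alcoholic beverage/day". Intake up to those limits is therefore eligible.
- **Alcohol marker** (section 7, Compliance monitoring): ethyl glucuronide is described as a "reliable marker of recent alcohol intake within the previous 5 days". It is tested at every meal pick-up, and a positive result leads to dismissal being considered.
- **Pick-ups** (section 7, Beverage and meal pick-up/return): subjects attend "two times/week to pick up a 3- or 4-day supply of meals/snacks/beverages".

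**The concern.** The check is meant to find sugar or alcohol taken during the study. A marker can do that only if its look-back lies wholly within the time on study diet. For the baseline delta-13C sample, the plan's own figures say that it does not. The Compliance monitoring section itself lists beverages sweetened with HFCS or cane sugar among the strongest sources of the signal, and eligible subjects may drink two sugar-sweetened beverages a day until the diet starts. Subjects are enrolled in weight reporting about two weeks ahead, but the text places no limit on their diet in that period.

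The consequence is fixed in advance. A high value removes the subject's data from the analysis, with no judgement about its source. A subject who kept to the diet could be lost for permitted intake. Those most exposed would be the heavier of the permitted sugar consumers and those with the shortest baseline.

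**Working it through.** **1. The plan's sample size, reproduced.** Section 8 (Sample Size) gives 24 per group for effect size 0.83, two-sided 0.05 and 80% power. A two-sample t-test needs n = 23.8, rounded up to 24, and power at 24 is 80.4%. The figure reproduces. It is not in dispute and is used only in step 4.

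**2. Delta-13C overlap.** Inputs: look-back 14 days (Compliance monitoring); baseline diet 9-13 days and intervention diet 28-33 days (General study design). I assume that the baseline drop is taken at the end of baseline, as the week-2 expectation implies. An earlier draw would enlarge the overlap.

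Pre-study days in the window = max(0, 14 − days on study diet at sampling).

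| Sample | Days on diet | Pre-study days | Share of 14 days |
|---|---|---|---|
| Baseline, longest | 13 | 14 − 13 = 1 | 1/14 = 7% |
| Baseline, shortest | 9 | 14 − 9 = 5 | 5/14 = 36% |
| End of intervention, shortest | 9 + 28 = 37 | 0 | 0% |
| End of intervention, longest | 13 + 33 = 46 | 0 | 0% |

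Zero overlap at baseline needs at least 14 days on diet, which is outside the stated range. The shares assume that each day counts equally. The documents give no weighting. The pre-study days are the oldest in the window, so if older days count less the shares are smaller.

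**3. Ethyl glucuronide overlap.** Inputs: look-back 5 days; pick-ups 3-4 days apart.

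Pre-study days = max(0, 5 − days on diet).

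- First on-diet pick-up, day 3 or 4: 5 − 3 = 2 or 5 − 4 = 1.
- Next pick-up, days 6-8, and all later ones: 0.
- Week-0 pick-up, if urine is tested then: all 5. Testing at every pick-up suggests that it is. The Table 2 schedule lists urine collection only in the rows that start at week 1.

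**4. Cost of a lost subject.** Two-sample t-test power at effect 0.83: 80.4% at 24 per group, 78.6% at 23, 76.7% at 22. The planned analysis is an ANCOVA, so these figures show scale only. How many subjects would be lost because of the look-back cannot be derived from the documents.

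**The case against.** The case on the other side has force, and much of it stands.

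- **The schedule is approximate.** The baseline range is itself qualified, and section 5 gives 40-47 days in total. With a 33-day intervention, 47 − 33 = 14 days of baseline is possible at the extreme. At 13 days the gap is one day against a rounded two weeks. So the overlap holds on the stated range, not for every conceivable subject.
- **The rule is relative.** Most subjects share some overlap, and the limit is set from their own mean and SD. Only unusual subjects are exposed.
- **The size is unknown.** A reader might infer that about one subject in 48 would be lost, since 48 × P(Z > 2) = 48 × 0.0228 = 1.1. That is the tail of any one-sided 2-SD rule on normal values, with or without overlap. It does not measure an excess caused by the look-back. Likewise, 2 × 1 = 2 to 2 × 5 = 10 permitted beverages in the window is a ceiling, with every day at the eligibility limit and equally weighted.
- **No bias between arms follows.** The baseline sample precedes the assigned beverage. Nor do the documents support saying that the trial loses the people it is about: the aims concern normal weight and overweight men and women, and eligibility was widened on age, BMI and metabolic values, not sugar habit.
- **The alcohol part is weak.** It targets routine drinkers, dismissal is discretionary, and the documents do not say that the 5-day window applies at the 500 ng/ml cut-off. Pick-ups every 3-4 days are no problem in themselves once a subject has been on the diet for 5 days.
- **A washout may have been given elsewhere.** Consent pages are not available, and the consent discussion and week-0 overview could include such an instruction.

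None of this reconciles a 14-day look-back with a 9-13 day diet, or exempts the baseline sample from an automatic exclusion.

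**Conclusion.** The point holds for the baseline delta-13C sample. On the stated range it covers about 1-5 days before the study diet (7-36% of the window under equal weighting, less otherwise). The statement that compliant subjects will all be low and comparable at the end of week 2 therefore does not follow from the plan's own figures, and the exclusion rule can remove a compliant subject for permitted intake. The end-of-intervention sample is unaffected.

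The harm is an unknown and probably small number of lost subjects; one fewer per group costs about 80.4 − 78.6 = 1.8 points of power. It is not a threat to the comparison between arms. The conclusion rests on the two-week look-back as the protocol states it, a draw at the end of a 9-13 day baseline, and no washout beyond the available text. The correction is worth making because the rule is automatic and the remedy is a few sentences.

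The ethyl glucuronide point is secondary. It concerns 1-2 pre-study days at the first on-diet pick-up, and all 5 only if urine is tested at week 0.

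**What to change.** In section 7, Compliance monitoring:

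1. Correct the sentence about compliant subjects so that it acknowledges the overlap at baseline.
2. State that a baseline delta-13C value drawn before 14 days on study diet does not by itself remove a subject from the analysis. Report it descriptively, or use it only with corroborating evidence from diet reports, returned food and body weights.
3. Keep the end-of-intervention sample as a trigger for exclusion, and state whether its mean and SD come from that time point alone.
4. Reconcile the 5-day ethyl glucuronide look-back with testing at every pick-up and with the discretionary dismissal wording, and make clear whether urine is tested at week 0.

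The cost is wording only, with no new samples. The downside is real and covers the whole baseline, not just its first days: with a 9-13 day diet, the sugar biomarker would essentially never exclude anyone on its own at baseline. Riboflavin does not fill the gap because it is carried in the intervention beverages. Baseline compliance would then rest on weights, returned food and diet reports.

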Experimental procedures: Procedures are performed as shown in the study schedule below (Table 2). This schedule is approximate and the 6-week length is approximate, as changes may

The effects of orange juice compared with sugar-sweetened beverage on risk factors and metabolic processes associated with the development of cardiovascular disease and type 2 diabetes

be made to accommodate subject availability and availability of the study facilities, equipment & personnel. Outpatient procedures will occur at the Ellison Building, University of California Davis Medical Center (UCDMC), and at Touro Metabolic Research Center (TMRC) in Vallejo, CA. Transportation from Davis to UCDMC and TMRC and will be offered by study using UCD Fleet Service vehicles. Subjects will be provided and required to wear a KN95 or N95 mask and face shield while in the vehicle and maintain a 6-foot distance from the driver and any other passenger. Participants who wish to provide their own transportation to the facilities will be reimbursed at the UCD mileage reimbursement rate. For subjects who provide their own transportation, a study staff commucation plan that will include a wake-up call if needed will be set up to ensure their arrival at TMRC or the Ellison Building on schedule.

The effects of orange juice compared with sugar-sweetened beverage on risk factors and metabolic processes associated with the development of cardiovascular disease and type 2 diabetes

Week	Procedure	Location	Time	Details	Compensation
Baseline ~ 2 weeks Energ			balanced baseline diet: carbohydrate (mainly starch50%Ereq), fat (35%Ereq) (15%Ereq)		
-2	Scale Pick-up	Ragle HNRC	TBD by subject	2 weeks prior to study start; at-home body weight scale pick-up visit	\$10
-2 - 6	Fasting BW	Home	pre-breakfast	Text, email or phone in fasting BW daily	\$65
0	Study Overview	Home	TBD by subject	Zoom meeting for study/schedule review & questions	\$10
0	1st Meal Pick-up	Ragle HNRC	TBD by subject	1st meal pick-up visit	\$10
1 - 2	Diet	Home/Ragle HNRC	TBD by subject	Daily consumption of provided baseline study meals Pick-up/dropoff for study meals; urine collection: 2 times/week	\$40
1	MRI#1	UCDMC Radiology	7:00	Hepatic & abdominal magnetic resonance imaging	\$50
1	Stool Collection #1	Home	TBD by subject	Stool collection	\$20
2	24-h UC #1	Home	TBD by subject	24 hour urine collection	\$30
2	Pre-TMRC Evening	Home	20:00, 23:00	Consumption of acetate tracer dose	\$40

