			7:00	Transport to TMRC, Consumption of acetate tracer dose	
			8:00	Check-in, vitals, anthropometrics, catheter insertion	
			8:45	Start blood collection every 30 or 60 minutes	
2	TMRC Visit #1	TMRC	9:00 - 12:00	Oral glucose tolerance test	\$150
			12:00	Lunch, Consumption of acetate tracer dose	
			13:00 - 15:00	Study questionnaires, DEXA scan	
			13:00 - 15:00 16:00	Study questionnaires, DEXA scan Dinner, Consumption of acetate tracer dose	
Interv	vention ~ 4 weeks	Energy-bala	16:00 20:00 anced intervention of	Dinner, Consumption of acetate tracer dose Final blood draw, remove catheter, check-out diet: Orange juice or SSB (25%Ereq), carbohydrate (ma Ereq), fat (35%Ereq), protein (15%Ereq)	inly starch
Interv	vention ~ 4 weeks	Energy-bala Home/Ragle HNRC	16:00 20:00 anced intervention of	Dinner, Consumption of acetate tracer dose Final blood draw, remove catheter, check-out diet: Orange juice or SSB (25%Ereq), carbohydrate (ma	inly starch \$140
		Home/Ragle	16:00 20:00 anced intervention of 25%	Dinner, Consumption of acetate tracer dose Final blood draw, remove catheter, check-out diet: Orange juice or SSB (25%Ereq), carbohydrate (ma Ereq), fat (35%Ereq), protein (15%Ereq) Consumption of provided intervention study meals & beverages Pick-up/dropoff for study meals/beverages; urine	
3-6	Diet	Home/Ragle HNRC	16:00 20:00 anced intervention of 25% TBD by subject	Dinner, Consumption of acetate tracer dose Final blood draw, remove catheter, check-out diet: Orange juice or SSB (25%Ereq), carbohydrate (ma Ereq), fat (35%Ereq), protein (15%Ereq) Consumption of provided intervention study meals & beverages Pick-up/dropoff for study meals/beverages; urine collection: 2 times/week	\$140
3-6	Diet 24-h UC #2	Home/Ragle HNRC Home	16:00 20:00 anced intervention of 25% TBD by subject TBD by subject	Dinner, Consumption of acetate tracer dose Final blood draw, remove catheter, check-out diet: Orange juice or SSB (25%Ereq), carbohydrate (ma Ereq), fat (35%Ereq), protein (15%Ereq) Consumption of provided intervention study meals & beverages Pick-up/dropoff for study meals/beverages; urine collection: 2 times/week 24 hour urine collection	\$140 \$40

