3-6 3 5 6 6	Diet 24-h UC #2 Stool Collection #2 24-h UC #3 MRI #2 Pre-TMRC Evening	Home/Ragle HNRC Home Home UCDMC Radiology Home	16:00 20:00 anced intervention of 25% TBD by subject TBD by subject TBD by subject TBD by subject 7:00 20:00, 23:00 7:00 8:00 8:45 9:00 - 12:00 13:00 - 15:00 16:00 20:00	Dinner, Consumption of acetate tracer dose Final blood draw, remove catheter, check-out diet: Orange juice or SSB (25%Ereq), carbohydrate (ma Ereq), fat (35%Ereq), protein (15%Ereq) Consumption of provided intervention study meals & beverages Pick-up/dropoff for study meals/beverages; urine collection: 2 times/week 24 hour urine collection Stool collection 24 hour urine collection Hepatic & abdominal magnetic resonance imaging Consumption acetate tracer dose Transport to TMRC; Consumption of acetate tracer dose Check-in, vitals, anthropometrics, catheter insertion Start blood collection every 30 or 60 minutes Oral glucose tolerance test Lunch, Consumption of acetate tracer dose Study questionnaires, DEXA scan	\$140 \$40 \$20 \$50 \$50 \$45

Procedure days are approximate and dependent on clinic and subject availability (baseline visits will occur in the first 2 weeks of the study and intervention visits will occur between the 5th and 6th week of the study)

Ragle HNRC: Ragle Human Nutrition Research Center at UCD campus, Department of Nutrition; UCDMC: University of California Davis Medical Center; TMRC: Touro (University) Metabolic Research Center; Ereq: energy requirement; BW: Body weight

The effects of orange juice compared with sugar-sweetened beverage on risk factors and metabolic processes associated with the development of cardiovascular disease and type 2 diabetes

Procedures at UCD or UCDMC:

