Urinary flavanone metabolites and catabolites: During baseline and two times during intervention study subjects will collect all urine over a 24-hour period. The urine collection period will begin with the first collection upon waking in the morning (no later than 9:00) and end at approximately 9:00 the next day. Subjects will be provided with pre-labeled bottles (enough to ensure all urine can be collected) containing a preservative solution (30 ml of 10% phosphoric acid) in a designated ice chest with enough cold packs to maintain refrigeration temperatures. Bottles will be transported to our laboratory in the designated ice chest (by either the subject or study staff). All collections are pooled by study staff, weighed and multiple aliquots are saved for metabolic analyses.

The pooled urine samples from baseline and from the two intervention collections will be assayed by the NIH West Coast Metabolomics Center at UC Davis for hesperetin-3'-sulfate, hesperetin-3'-O-glucuronide, 3-(3'-hydroxy-4'-methoxyphenyl)hydracrylic acid, hesperetin-7-O-glucuronide, naringenin-4'-O-glucuronide and naringen-7-O-glucuronide using liquid chromatography-high resolution mass spectrometry ⁸³. Standards for each compound will be obtained from Toronto Research Chemicals (Toronto, Canada). All outcomes will be adjusted for urinary creatinine concentration, which will be measured on a PolyChem Chemistry Analyzer.

Abdominal and hepatic fat/fasting blood sample: A fasting Magnetic Resonance Imaging (MRI) for hepatic lipid content and quantification of visceral and subcutaneous fat will be performed at the beginning and at the end of the study at the UCDMC Department of Radiology. These appointments are usually scheduled at 7:00 and study staff provide transport in university vehicles to subjects. Due to the pandemic, some subjects may prefer to drive themselves, and these subjects will be reimbursed at the UCD mileage reimbursement rate. Female participants will have a urine pregnancy test prior to the MRI. [name], Department of Radiology UCD Medical Center, will supervise the pre- and post- quantification of images for intra-/extra-abdominal fat. Image post-processing, tissue segmentation, and analysis of liver fat will be performed by Post-doctoral fellow [name] using a commercial semi-automated software tool (SliceOmatic; Tomovision, Inc.).

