Microbiome - Fecal collection: Each subject will receive instructions and a sample collection kit containing ice packs, labeled sample vials, a fecal collection kit, zip-lock bags, and a sealable secondary container (freezer box). Feces will be collected in a disposable fecal collection vessel that attaches to the toilet. Subjects will be instructed to label sample vials with date and times of sample production. Subjects will transfer approximately 10mL of sample into the sample vials using the scoop that is attached to the sample vial lid. The lid is replaced on sample vial and the vial is placed in the ziplock bag and then in the secondary container and stored in the subject's freezer until subject is ready to transport sample back to UC Davis. Upon arrival at UC Davis, labeled sample will be placed in a -80°C freezer until processed for future analyses. Subjects will be asked to collect one sample during baseline and one sample during the intervention period.

The effects of orange juice compared with sugar-sweetened beverage on risk factors and metabolic processes associated with the development of cardiovascular disease and type 2 diabetes

Procedures at TMRC: These tests will be conducted during a 13-hour period at TMRC, which will occur during the baseline period and be repeated 4 weeks later during the intervention period.

Isotope consumption for assessment of DNL (Figure 1): We are replacing our original 26-hour isotope infusion protocol with an oral bolus protocol. Each subject will be provided with two doses of an oral stable-isotope tracer (1-¹³C acetate) in water that will be consumed at 20:00 and 23:00 the night before the outpatient visit to the TMRC. Subject will be picked up at 6:30 - 7:00 by study staff for transport to TMRC. Due to the pandemic, some subjects may prefer to drive themselves to TMRC, and these subjects will be reimbursed at the UCD milage reimbursement rate. A third dose of the acetate tracer will be consumed at 7:00. Additional doses of acetate tracer will be provided and consumed at the TMRC at 9:00, and with meals at 12:00 and 16:00. Each oral dose of the acetate tracer will consist of 1-2 grams 1-¹³C acetate in approximately 4 ounces of water.

Blood pressure: Blood pressure will be measured at check-in, before dinner, and prior to check-out. Weight, height, waist and hip will be measured.

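### The baseline MRI is scheduled in week 1, so the change in liver and visceral fat covers part of the low-sugar run-in as well as the beverage period

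*Combined protocol and SAP*

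**What the plan says.** In section 7 (Procedures at UCD or UCDMC, paragraph on abdominal and hepatic fat), the fasting MRI "will be performed at the beginning and at the end of the study at the UCDMC Department of Radiology". Table 2 places the first scan in week 1: "1 MRI#1 UCDMC Radiology 7:00", described as "Hepatic & abdominal magnetic resonance imaging". The same table puts the baseline 24-hour urine and the baseline TMRC visit (OGTT, de novo lipogenesis, blood profiles, DEXA) in week 2: "2 TMRC Visit #1 TMRC 9:00 - 12:00". The text on the TMRC tests gives their spacing: "which will occur during the baseline period and be repeated 4 weeks later during the intervention period".

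The run-in is described under General study design: "All subjects will consume a provided, standardized, low sugar, energy-balanced diet for approximately 9-13 days". The intervention then lasts about 28-33 days. The Table 2 footnote makes procedure days approximate: "baseline visits will occur in the first 2 weeks of the study and intervention visits will occur between the 5th and 6th week of the" trial.

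Section 6 names hepatic lipid content as a secondary endpoint. The data analysis plan in section 8 takes the change from baseline as the dependent variable. It fits an analysis of covariance adjusted for BMI and the baseline value, and it also declares a change from baseline significant when an adjusted mean differs from zero. Baseline liver fat and visceral fat are listed there as candidate covariates for other outcomes.

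**The concern.** The run-in puts every subject on the same low-sugar diet before the beverage starts. The week-2 measurements are taken after most of it; a week-1 scan is not. Section 4 excludes "routine ingestion of more than 2 sugar-sweetened beverages or 1 alcoholic beverage/day", so a subject may enter with habitual intake up to those limits. During the study only the provided food and drink are allowed. An early scan may therefore reflect a dietary state that differs from the one just before the first beverage, and the later change would include whatever happened in between.

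Three things are at stake:

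- **Within-arm change.** The test against zero would be read as a beverage effect, although for MRI outcomes it covers run-in plus beverage.
- **Precision.** If subjects respond differently to the run-in, that variation enters the change score and can weaken the baseline scan as a covariate.
- **Comparability across Aim 2.** Liver fat would not share a baseline state with de novo lipogenesis and insulin sensitivity, the other processes named in that aim.

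**Working it through.** **1. The plan's own figure.** The sample-size paragraph gives 24 per group for a standardised difference of 0.83, two-sided 5%, 80% power. The normal approximation gives n = 2(1.96 + 0.8416)²/0.83² = 22.8, so 23. The two-sample t-test gives 23.8, so 24, with 80.4% power at 24 per group. The figure reproduces. It is justified there by LDL-C, apoB and uric acid; none is given for liver fat.

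**2. Share of the MRI interval that is run-in.** Inputs: run-in R = 9 to 13 days and intervention I = 28 to 33 days (General study design). Assume the second scan is on the last intervention day. With d diet days completed before the first scan, share = (R − d)/(R − d + I).

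| R | I | Scan at start of run-in (d = 0) | Scan after 7 diet days (d = 7) |
|---|---|---|---|
| 9 | 28 | 9/37 = 24% | 2/30 = 7% |
| 9 | 33 | 9/42 = 21% | 2/35 = 6% |
| 13 | 28 | 13/41 = 32% | 6/34 = 18% |
| 13 | 33 | 13/46 = 28% | 6/39 = 15% |

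A day-1 scan thus gives an interval of 37-46 days, 21-32% of it run-in; a day-7 scan gives 6-18%. If the day-7 scan is taken in the morning with six diet days completed, the range is 3/36 = 8% to 7/35 = 20%. A scan at the end of the run-in gives about 0% and an interval of 28-33 days. A second scan before the last intervention day raises every share.

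**3. Expected between-arm difference.** Write each subject's change as run-in response plus beverage response. Both arms follow the same run-in and allocation is randomised, so the mean run-in response cancels from the arm difference.

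**4. What a run-in response could do (assumed values).** The documents give no such response, so the sizes below are chosen for illustration, in units of the SD of change.

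- *Within one arm of 24, no beverage effect, mean run-in shift r.* A one-sample t-test, as a simple stand-in for the adjusted-mean test, has noncentrality r√24. It is significant with probability 5% at r = 0, 22% at 0.25, 65% at 0.50 and 94% at 0.75. A shift opposite in sign to a real beverage effect would hide that effect.
- *Between arms, run-in responses varying with SD s, independent of the rest of the change.* The standardised effect becomes 0.83/√(1 + s²).

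| s | Effect | Power, 24 per group |
|---|---|---|
| 0 | 0.830 | 80% |
| 0.25 | 0.805 | 78% |
| 0.50 | 0.742 | 71% |
| 0.75 | 0.664 | 62% |

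The 0.83 is borrowed from other outcomes, so this shows how precision could fall; it is not a power estimate for liver fat.

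**The case against.** The strongest reply is that the schedule is explicitly approximate. The footnote allows baseline visits anywhere in the first two weeks, and the Specific Aims text says only that liver lipid is assessed during baseline and at the end of intervention. The wording on the beginning and end of the study may be ordinary pre/post language, and with a nine-day run-in a day-7 scan is close to its end. This stands as far as it goes: a day-1 scan is not a rule, and neither is any fixed interval between scans. But the flexibility makes run-in exposure vary from subject to subject. Nothing sets a minimum number of diet days before the scan or adjusts for them.

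A second reply is that no run-in response is documented. That is correct. A reader might infer that liver fat falls during the run-in, so that within-arm changes are shifted downward. The diet is energy-balanced, the beverage and alcohol limits are ceilings for entry and not typical intakes, and no passage gives a direction. A reader might also infer a large loss of precision from an assumed fall in the baseline to end-of-study correlation. From 0.95 to 0.90 the residual SD would rise by √(0.19/0.0975) = 1.40 times, but from 0.80 to 0.78 by only √(0.3916/0.36) = 1.04 times. The documents supply no correlation, so neither figure can be claimed.

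Third, the Aim 2 hypothesis compares the two beverages, and there is no arm without a beverage. Even a week-2 scan would leave within-arm change open to other influences over time. This also stands: a later scan removes one identifiable component, not all of them. The plan nevertheless tests within-arm change, so the component matters.

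Finally, week 2 is crowded. With a nine-day run-in it has two days, and it already holds the urine collection, the tracer evening and the long TMRC visit. This argues for flexible wording on the scan date, not for leaving it in week 1.

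**Conclusion.** The point holds as a limited but inexpensive improvement. As scheduled, roughly 6% to 32% of the interval behind the hepatic lipid and visceral fat change is run-in, depending on the scan day and the lengths of the two periods. This rests on the stated day ranges and a second scan at the end of intervention. For these outcomes, the test of adjusted mean change against zero cannot be attributed to the beverage period alone.

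A reader might conclude that the orange juice versus sugar-sweetened beverage comparison is biased. The documents do not support that, because the run-in is common to both randomised arms; the possible cost there is precision, of unknown size. The blood lipid outcomes from the TMRC visits have their baseline in week 2 and are not affected in this way. Hepatic lipid is a secondary endpoint, which limits the weight of the point.

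**What to change.** - **Subjects still to be enrolled.** In Table 2, schedule the first MRI as late in the baseline period as booking allows, near the baseline TMRC visit and before the first beverage. In section 7, replace the reference to the beginning and end of the study with the end of the low-sugar baseline period and the end of intervention.
- **Subjects already scanned early.** Record the days from the first MRI to the first beverage and add them as a covariate in a sensitivity analysis of liver and visceral fat. If most early scans fall on similar days, or if timing shifts partway through enrolment, this covariate will carry little information or will track calendar time. It should therefore not replace the main model.
- **Interpretation.** State in section 8 that conclusions on liver and visceral fat rest on the between-arm contrast, and that within-arm change is descriptive for these outcomes.

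No additional scan is needed. The cost is tighter radiology booking in week 2 and scan timing that differs from subjects who have already completed.
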